This is an open-label study where all subjects are to receive the Study drug. The study will enroll to treat a minimum of 20 subjects, 2 years of age and older, presenting with 1-6 common warts with the goal of approximately 20 subjects completing all study activities in Cohort 1 per protocol. Cohort 2 will utilize up to 4 sites to enroll approximately 35 subjects (12 years and older). Although no formal power calculations have been performed, it is expected that a sample size of 20 subjects (Cohort 1) and 35 subjects (Cohort 2) evaluable at the EOS/EOT visit (Day 84 for both Cohorts) will be informative regarding wart clearance rates that can support assumptions in subsequent placebo-controlled trials. A sample size of 20 completed subjects for Cohort 1 and approximately 35 subjects for Cohort 2, will provide information to build an adequate safety profile of VP-102 in common warts. The primary analysis will be conducted at Day 84 for both Cohorts. The final analysis will be conducted for Cohort 2 when the last patient has completed the visit on Day 147.

Subjects who receive all planned treatments of VP-102 (e.g., up to four treatments within the 63 day treatment window, or cleared of all treatable warts prior to Day 63 in Cohort 1; and in Cohort 2 complete up to four treatments within the Day 75 treatment window or clear prior to Day 75) and have no major protocol violations are assessed for clearance at the EOS visit and included in the Per Protocol population.

Subject demographics, efficacy tables and subject dropout rates will be tabulated at the end of the study. Data will be summarized using descriptive statistics (sample size, mean, median, standard deviation, minimum, maximum) for continuous variables and frequencies and percentages for discrete variables. Corresponding by-subject data listings will be tabulated.

Adverse events, including local skin reactions, will be coded with the MedDRA® dictionary. The number and percentage of subjects having treatment-emergent AEs will be tabulated by system organ class and MedDRA preferred term with a breakdown by treatment group.

Table 1 Study Schedule of Assessments and Procedures – Cohort 1

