2.2.2 Clinical Studies with Cantharidin

Cantharidin has been used by healthcare providers for decades to treat Verruca vulgaris. The following summarizes completed and/or ongoing safety and efficacy studies conducted with VP-102.

VP-102 prospective studies

A 12-week, open-label Phase 2 study was implemented under IND 131163/NCT03186378. Subjects ≥ 2 yrs old with Molluscum contagiosum (MC) were enrolled and treated with VP-102, a single-use proprietary applicator containing a novel 0.7% w/v cantharidin solution, every 21 days for up to 4 treatments or until complete lesion clearance. Subjects were instructed to wash VP-102 off at 24 hrs, or earlier if significant pain or blistering. Lesion counts and adverse events (AEs), including local skin reactions, were documented at each visit. Quality of life (QoL) was measured using the Children's Dermatology Life Quality Index (CDLQI). A subset of 17 subjects with ≥ 21 MC lesions at Baseline were evaluated for systemic exposure with 4 blood samples (pre-VP-102 and 2, 6, & 24-hrs post). Key efficacy endpoints were % subjects exhibiting complete clearance of all treated MC lesions (baseline and new) on or before Week 12 and % reduction of treated MC lesions from Baseline at Week 12.

The mean age was 7.3 (range=3-15) yrs for the 33 subjects enrolled, with 32 completing the study. A total of 29 subjects (88%) reported at least one AE including expected local skin reactions such as blistering or erythema with no serious adverse events (SAEs). Sixteen subjects (50%) achieved complete clearance of all MC lesions on or before Week 12. The median lesion count was reduced from 23 (range 3-113) at Baseline to 1 (0-95) at Week 12 ($p < 0.0001$). Plasma drug levels were below the limit of quantitation in 65 of 66 samples. In one subject, the level was slightly above the lower limit of quantitation 2 hrs after VP-102 application, but not detectable at 6 & 24 hrs. The mean \pm SD CDLQI score was notably improved from 2.6 \pm 3.4 at Baseline to 0.4 \pm 0.9 at Week 12.

Treatment with VP-102 was well-tolerated and associated with significantly reduced lesion count, improved QoL and complete clearance of MC lesions in 50% of subjects.

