A bridging study, conducted under IND #114032, was implemented to confirm VP-102's similarity in safety and efficacy to a 0.7% compounded cantharidin formulation used previously under the same IND. For this study, VP-102 was packaged in single-use screw-top vials and applied with the wooden part of a cotton-tipped swab to two cohorts of subjects. The first cohort investigated a 6-hour treatment duration. In the 6-hour cohort, 14 subjects were enrolled, and 13 subjects completed all study visits. A second cohort investigated a 24-hour treatment duration. In this cohort, 16 subjects were enrolled, and 12 subjects completed all study visits. Overall, eleven subjects showed complete clearance out of 25 subjects in the per protocol population (PPP) (44 % clearance).

In this bridging study, there were no unexpected treatment related adverse events reported during application to 1,0 molluscum lesions in 14 subjects in the 6-hour cohort. Moreover, there were no treatment related adverse events reported with application to 712 lesions in 16

subjects in the 24-hour exposure to VP-102. Thus, this bridging study demonstrated that VP-102 appears to be safe and well tolerated in the treatment of pediatric molluscum, consistent with historically used cantharidin formulations.

The following summarizes significant prospective studies using compounded cantharidin as a treatment modality and documenting safety in molluscum contagiosum and both efficacy and safety in common warts.

Additional clinical information on the safety of cantharidin comes from over 50 years of experience with cantharidin (0.7% w/v) as a treatment for molluscum and warts. In all of these studies, the most commonly reported adverse events were blistering and pain at the site of application consistent with the pharmacologic activity of cantharidin. More infrequently rash, pruritus, pigment changes, ring warts and secondary infections were reported.

(Studies utilizing cantharidin for treatment of warts have been limited however all have shown either reduction or clearance over the course of one or several treatments. Treatment with 0.7% cantharidin has been safe and well tolerated in the treatment of common warts when used under the guidance of a trained medical professional. Below are several studies outlining the efficacy and safety profile using compounded cantharidin and in some instances, occlusive tape.

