4.4 Enrollment & Dropouts

Pre-study screening for eligibility (informed consent and assent [when applicable]), demographics, physical exam, prior and current concomitant medications, dermatologic exam with Fitzpatrick skin type, wart and medical history can occur up to 14 days before, or on the same day as the first Study drug application. The wart count (Cohort 1), measurements, location of all warts, ERT and photos must be repeated if not conducted on the same day as treatment. Subjects that do not continue to meet criteria at Treatment Visit 1 will be discontinued and treated at physician discretion per standard of care. Those subjects that meet the enrollment criteria will be treated with application of VP-102 at Treatment Visit 1. Treatment will continue with a minimum of 14 days between treatment until complete clearance or a maximum of 4 treatment sessions. The exact treatment interval will be determined by evaluation of the treatment site and take any ongoing LSRs into account. For subjects that achieve complete clearance or all treatable warts prior to Treatment Visit 4, ERT phone calls will be conducted at the required 2-week treatment intervals to assess the status of any AE's or skin reactions since the last visit and confirm there has been no recurrence in treated warts or new warts have developed. Subjects that report recurrence of, or presence of new warts, will be scheduled for a Treatment Visit per protocol. *(Sites should consider calling the subject a few days prior to the 2-week interval (e.g., 11 or 12 days) to ensure adequate time for scheduling assessment and treatment if needed.)*

The Day 84 EOS Visit will require a final assessment of ERT (for Cohort 1) and confirmation of the presence or absence of treated and untreated warts as well as the final size and diameter for any that are remaining. Subjects in Cohort 2 will participate in an in-person EOT evaluation at Day 84 (- 0/+ 8 days). A provider EOT Questionnaire will be completed at the EOT Visit. Cohort 2 subjects will continue in the study for 3 additional follow-up assessments on Day 105, Day 126 and Day 147. Each investigator conducting this final wart assessment, must be a study qualified member of the research team.

REPLACEMENT OF DROPOUTS

Subjects who do not complete the EOS/EOT assessment will be considered dropouts. Subjects who are enrolled in the study but never receive study drug will also be considered dropouts. Dropouts will not be replaced.

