9.2.6 Sample Size

The study will enroll subjects with common warts for the main purpose of obtaining information on clearance rates of the warts in response to VP-102 therapy. Subjects in Cohort 1 will continue to be enrolled in the study to a target of approximately 20 subjects completing the EOS visit. In Cohort 2, approximately 35 subjects will be enrolled.

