The study will enroll subjects with common warts for the main efficacy purpose of obtaining information on clearance rates of the warts in response to VP-102 therapy. Subjects will continue to be enrolled into Cohort 2 of the study until approximately 35 subjects are enrolled. Due to the exploratory nature of the study, no formal sample size estimates will be carried out for powering purposes.

5. Statistical Methods

The statistical analyses described in this document are specific to Cohort 2 of this study and will be reported using summary tables, figures and listings (TFLs). Numbering for TFLs will be based on the recommended numbering convention provided by the International Conference on Harmonization. Continuous variables will be summarized with means, standard deviations, medians, minimums and maximums. Categorical

variables will be summarized by counts and percent of subjects in corresponding categories. Where appropriate, 95% confidence intervals may be included. Missing values are not considered for percent calculations, unless stated otherwise. In those cases, footnotes will specify the percent basis.

Individual subject data obtained via the electronic data capture (EDC) system and from external vendors will be presented in listings.

The analyses described in this plan are considered *a priori*, in that they have been defined prior to database lock. Any analysis added after the database lock will be considered *post hoc* and exploratory. *Post hoc* analyses will be labeled as such on the output and identified in the CSR. All analyses and tabulations will be performed using SAS® version 9.3 or higher. Tables and listings will be presented in .rtf or .pdf format. Upon completion, all SAS programs will be validated by an independent programmer. The validation process will be used to confirm that statistically valid methods have been implemented and that all data manipulations and calculations are accurate. Checks will be made to ensure accuracy, consistency with this plan, consistency within tables and consistency between tables and corresponding data listings.

6. Analysis Populations

Intent to Treat (ITT) Population:

The Intent-to-Treat population (ITT) will include all subjects enrolled in the study.

Per Protocol Population:

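### Cohort 2 is justified by 35 subjects evaluable at Day 84 but enrols only about 35, with no attrition allowance and conflicting replacement rules

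*Protocol*

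**What the plan says.** **Size.** The Statistical methods part of the protocol Synopsis says that no formal power calculation was done. It then expects that "35 subjects (Cohort 2) evaluable at the EOS/EOT visit" will be informative about clearance rates for later placebo-controlled trials. The same paragraph gives the Cohort 2 enrolment figure, which is also about 35.

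The dedicated sample-size sections give Cohort 2 an enrolment figure only. Protocol 9.2.6: "In Cohort 2, approximately 35 subjects will be enrolled". SAP section 4: "Subjects will continue to be enrolled into Cohort 2 of the study until approximately 35 subjects are enrolled". For Cohort 1, protocol 9.2.6 instead enrols "to a target of approximately 20 subjects completing the EOS visit".

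**Replacement.** Protocol 4.4 counts a subject without the EOS/EOT assessment as a dropout and says "Dropouts will not be replaced". The paragraph that follows says that subjects who stop through non-adherence or at their own request are replaced. It says the same of subjects who leave because of study-related adverse experiences or spreading disease, who are also analysed as treatment failures. SAP 8.4 treats that last group as failures but does not replace them. It has no rule on replacing anyone else.

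**Analysis.** Protocol 9.2.2 and 9.2.3 make the intent-to-treat (ITT) population, all enrolled subjects, the primary set. Protocol 9.2.7 and SAP 8.4.1 count a missing clearance assessment as not cleared. The Per Protocol set requires a clearance assessment at the end-of-treatment visit (SAP section 6).

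**The concern.** One number stands for two different quantities. Every dropout, as protocol 4.4 defines the term, is one subject fewer evaluable at Day 84. About 35 enrolled therefore cannot also mean 35 evaluable unless losses are nil or are made good. The protocol avoids the problem in Cohort 1 by enrolling to a completer target, and does not carry that device over to Cohort 2.

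At stake is the only stated efficacy rationale for the cohort's size. Someone using the result to plan the next trial needs to know whether 35 is the enrolled or the assessed number, and how precise each rate will be. While the replacement rules disagree, neither the final enrolment nor the expected evaluable number is defined.

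**Working it through.** **The plan's own figure.** The documents give no alpha, power, effect size, precision target or dropout rate, so there is no formula to reproduce. The available check is whether 35 enrolled yields 35 evaluable. With dropout proportion d and no replacement:

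- expected evaluable = 35 × (1 − d)
- chance that all 35 are evaluable = (1 − d)^35, assuming independent losses

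At d = 0 the first gives 35, which is the stated figure.

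**Attrition inputs.** The only VP-102 completion data in the documents are the molluscum studies in protocol 2.2.2. They serve here as assumptions:

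- 12-week open-label study, 33 enrolled, "with 32 completing the study": d = 1/33 = 3.0%
- bridging study, 6-hour cohort, 13 of 14 completed: d = 1/14 = 7.1%
- bridging study, 24-hour cohort, "In this cohort, 16 subjects were enrolled, and 12 subjects completed all study visits": d = 4/16 = 25%
- pooled: (32 + 13 + 12)/(33 + 14 + 16) = 57/63 = 90.5% completing, d = 9.5%

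**Expected evaluable out of 35, no replacement**

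| Completion | Expected evaluable | Chance all 35 evaluable |
|---|---|---|
| 32/33 | 35 × 32/33 = 33.9 | 34% |
| 13/14 | 35 × 13/14 = 32.5 | 7% |
| 57/63 (pooled) | 35 × 57/63 = 31.7 | 3% |
| 12/16 | 35 × 12/16 = 26.3 | below 0.01% |

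**Precision.** The Clopper-Pearson 95% limits for x cleared of n are the 2.5% quantile of Beta(x, n − x + 1) and the 97.5% quantile of Beta(x + 1, n − x). Near 50% clearance:

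| n | x | 95% limits | Half-width |
|---|---|---|---|
| 35 | 18 | 34.0% to 68.6% | 17.3 points |
| 34 | 17 | 32.4% to 67.6% | 17.6 points |
| 32 | 16 | 31.9% to 68.1% | 18.1 points |
| 26 | 13 | 29.9% to 70.1% | 20.1 points |

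The cost relative to 35 is 18.1 − 17.3 = 0.8 points at the pooled rate and 20.1 − 17.3 = 2.8 points at the worst rate.

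**Replacement rules side by side**

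| Reason for leaving | Protocol 4.4, dropout paragraph | Protocol 4.4, next paragraph | SAP 8.4 |
|---|---|---|---|
| Non-adherence, or own request | not replaced | replaced | silent |
| Adverse experience or spreading disease | not replaced | replaced | not replaced |
| Lost to follow-up | not replaced | not named | silent |

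Under the dropout paragraph, 35 enrolled gives 35 evaluable only with no losses. Under the next paragraph, the named losses are made good, but each replacement is a further enrolment. Because treated dropouts stay in the ITT set, that set then grows beyond 35. To end with 35 evaluable, total enrolment would have to be ceil(35/(1 − d)): 37 at 3%, 39 at the pooled rate and 47 at 25%.

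**The case against.** The strongest reply is that nothing here is a commitment. The study is descriptive and unpowered, the 35 evaluable is an informal expectation in one Synopsis sentence, and enrolment is approximate throughout. That is fair: one or two losses, as at 3% to 5% dropout, fit within the word approximately. At 10% the expected number is 35 × 0.90 = 31.5, a shortfall of 3.5, which does not fit comfortably.

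A second reply is that the primary analysis is untouched. This stands. The ITT denominator remains about 35 because a missing assessment counts as not cleared. The wider interval belongs to a rate among those assessed at Day 84, which is not itself a planned analysis. The Per Protocol set has further exclusions, so 26 to 34 is not its size either. Confidence intervals are optional in the SAP.

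A third reply is that the attrition inputs are borrowed. They come from molluscum, not from common warts in subjects aged 12 and over. Completing all visits is also not the same as being assessed at Day 84, and the 25% rests on 16 subjects. This stands too, and it is why the range is presented as an assumption.

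A reader might infer that any dropout at all makes the plan miss 35 evaluable, because nobody is replaced. The documents do not support that as the settled rule. Protocol 4.4 goes on to replace several kinds of discontinuation, and SAP 8.4 bars replacement for one kind only. A reader might also infer that every lost subject lowers the ITT clearance rate. That is true only of a subject who would have cleared, and it follows from the missing-data rule, not from the sample-size wording.

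**Conclusion.** The inconsistency is real and limited. The Synopsis argues from 35 evaluable, the design provides for about 35 enrolled, and no attrition allowance connects the two. Contradictory replacement rules leave it open whether the gap is meant to be filled.

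If nobody is replaced and attrition lies between 3% and 25%, about 34 down to 26 of 35 would be assessed at Day 84, with about 32 as the pooled figure. The half-width for a rate among those assessed would be about 18 to 20 points instead of about 17. These figures assume clearance near 50%, exactly 35 enrolled, and completion like that in the cited molluscum studies.

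The documents do not show that the primary analysis loses precision or that the cohort is too small for its purpose. The correction is worth making because it is cheap and concerns the only efficacy argument given for the cohort's size.

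**What to change.** 1. In the Synopsis, Statistical methods, state that 35 is the approximate enrolled (ITT) number for Cohort 2. Add the expected number evaluable at Day 84 under a named attrition assumption, for example about 34 down to 26 for 3% to 25% attrition, or about 32 at the pooled 57/63, identified as coming from molluscum studies.
2. Give the expected precision there: an exact 95% half-width near 50% clearance of about 17 points for the ITT rate (n = 35) and about 18 to 20 points for a rate among those assessed at Day 84.
3. Reconcile the two paragraphs of protocol 4.4 and SAP 8.4 into one replacement rule that covers every reason for leaving, including loss to follow-up. If any replacement is kept, say that enrolment and the ITT set may exceed 35.

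The cost is a few sentences in the protocol and a matching one in SAP 8.4. SAP section 4 already describes 35 as enrolled and needs no correction to its figure. Restating 35 as the enrolled number needs no extra patients. Only a deliberate choice to guarantee 35 evaluable would raise enrolment.

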Table 2	Study Schedule of Assessments and Procedures - Cohort 2.....	20
Table 3	Classification of AEs by Intensity	66
Table 4	Assessment of Causality of AEs	67
Table 5	Timeline for Reporting of SAEs.....	68

LIST OF IN-TEXT FIGURES

Figure 1	Clinical Trial Labeling of Study Drug	51
----------	---	----

LIST OF ABBREVIATIONS

Abbreviation	Definition
AE	Adverse event
AMES	Genetic toxicity study: in vitro bacterial reverse mutation
CDLQI	Children’s dermatology life quality index
cm	Centimeter
Con Meds	Concomitant medications
COVE	Cantharidin and Occlusion in Verruca Epithelium
eCRF	Electronic case report form
EOS	End of study
EOT	End of Treatment
EDC	Electronic data capture
ERT	Evaluation of response to treatment
FDA	Food and Drug Administration
GLP	Good laboratory practice
GMP	Good manufacturing practices
HIPAA	Health Insurance Portability and Accountability Act
HPV	Human papilloma virus
IB	Investigator Brochure
ICF	Informed consent form
ICH	International Council for Harmonisation
ID	Identification
IFU	Instructions for use
IND	Investigational new drug application
I.P	Intraperitoneal
IRB	Institutional review board
ITT	Intent to treat
I.V	Intravenous
LSR	Local Skin Reaction
MC	Molluscum contagiosum
MOP	Manual of Operations
mg	Milligrams
mm	millimeter
Molluscum	Molluscum contagiosum
PPP	Per protocol population
QoL	Quality of life
SAE	Serious adverse event
SOP	Standard operating procedure
TEAE	Treatment emergent adverse event
TSGH 8301	Human urinary bladder carcinoma cell line

uL	Microliters
VP-102	Verrica Pharmaceuticals-102 (0.7% w/v cantharidin)
Veruca	Verruca vulgaris (common warts)
W/V	weight/volume

2 INTRODUCTION

2.1 Verruca Vulgaris (common warts)

Cutaneous viral warts (*Verruca vulgaris*) are caused by the human papilloma virus (HPV) and are a common problem with an estimated lifetime incidence of 79% (1). There are over 100 known serotypes of HPV in humans alone, with a growing number discovered each year. The majority of cutaneous warts are caused by HPV serotypes 1, 2, 3, 4, 7 and 10 (2). HPV is a DNA virus, which infects epithelial cells. Viral replication only takes place in fully differentiated epithelium and the subsequent proliferation results in a clinically evident hyperkeratotic papule or plaque.

The clinical appearance of warts is variable and depends to some extent on the serotype of HPV involved and the anatomical site. HPV has a histone-coiled, double-stranded DNA genome of approximately 8,000 base pairs. This genetic material is surrounded by a 60-nanometer capsid composed of two interlocking proteins (L1 & L2), but no envelope (3). This lack of an envelope gives the virus significant stability in the environment, allowing it to remain a viable infectious agent for weeks, or even months before coming in contact with a suitable host (4). Any epithelial surface can be affected, and different types of HPV tend to favor particular anatomical sites, but the most common infections are with HPV type 2 on the hands and feet. In general, viral warts are uncommon in infancy, increasingly common in childhood, reach a peak in the teenage years and decline sharply in prevalence thereafter. Non-genital warts in immunocompetent people usually resolve spontaneously with time, but this can take years.

The rate of resolution depends on a number of factors including host immunity, HPV type, and site of infection. Although usually benign, warts are an infectious disease of the skin that should be treated to prevent transmission of the virus from person to person or autoinoculation to multiple sites on the same individual. In addition, verrucae can cause pain or discomfort, interfering with work or daily activities (5). Warts are frequently considered cosmetically unsightly, and unacceptable to the subject, particularly if they occur on visually prominent areas like the face, neck, arms or hands. Importantly, the possibility of squamous cell carcinoma of the skin is believed to be enhanced by the presence of HPV, especially on skin damaged by extensive UV exposure. This effect has been well documented in individuals with epidermodysplasia verruciformis, immunosuppressed individuals, and transplant recipients; however, it is also suspected to play a role in some cases of squamous cell carcinoma in immunocompetent individuals (6-8).

There are a wide variety of different treatments for warts, but most are of limited effectiveness. Ablative and surgical treatments are among the most commonly used, with their mode of action being the destruction of the wart through physical means (e.g., cryotherapy, electrodesiccation with or without curettage, lasers, infrared photocoagulation); surgical modalities (e.g., blunt dissection, excision); and organic acids/keratolytics (e.g., salicylic acid, bi- or trichloroacetic acid, urea).

Other published modalities attempt to modify the way the skin and immune system interact with the infection, such as immunomodulators (e.g., imiquimod, intralesional interferon,

mumps vaccine, human α -lactalbuminoleic acid, cimetidine, levamisole) and allergens (e.g., diphenylcyclopropanone, Candida extract, squaric acid dibutylester). Some therapies attempt to directly interfere with infected cell proliferation, like cytotoxins (e.g., bleomycin, 5-fluorouracil, podophyllotoxin, aminolevulinic acid) and vesicants (e.g., cantharidin). Some studies have suggested the use of simple occlusion with impermeable tape, although the efficacy of this has recently been shown to be lacking (9). The large number of treatment options reflects the lack of consensus among experts on what the best treatment for common warts is, despite the fact that common warts are seen so often in dermatology and primary care clinics. Expert reviews fail to find that any one treatment is considerably better than the others (2, 10), and most authors agree that adequate clinical studies are lacking for many of the treatments, including those considered first line (9, 11) and newer modalities that are being used in an “off-labeled” approach to treatment (12).

The two most commonly used treatments for cutaneous warts are salicylic acid and aggressive cryotherapy. A Cochrane meta-analysis of 6 randomized clinical trials with a combined 486 patients evaluating efficacy found topical salicylic acid to have a cure rate of 57% vs 37% with placebo ($p < 0.001$). For cryotherapy, a meta-analysis of 3 randomized clinical trials involving a total of 227 patients showed a cure rate of 38% vs 22% with placebo ($p = \text{NS}$) (9). Salicylic acid therapy, while effective, requires daily compliance and can cause a painful burning sensation. Cryotherapy has limited efficacy and is very painful, so much so that most physicians do not treat children with cryotherapy if they have other options. Both of these therapies have the potential to leave long-term scars. Unfortunately, in many cases patients are dissatisfied with their outcomes, with some studies showing this to be the case up to 91% of the time (13). This is cause for concern, as the common wart is ranked among the most frequent reasons that individuals seek evaluation in a dermatology practice (14) and can represent a significant cost to the patient and insurer (1).

